9.2.7 Potential Drug Induced Liver Injury (DILI)

Wherever possible, timely confirmation of initial liver-related laboratory abnormalities should occur prior to the reporting of a potential DILI event. All occurrences of potential DILIs, meeting the defined criteria, must be reported as SAEs (see [Section 9.2](#) and [Appendix 3](#) for reporting details).

Potential drug induced liver injury is defined as:

- AT (ALT or AST) elevation > 3 times upper limit of normal (ULN)
AND
- Total bilirubin > 2 times ULN, without initial findings of cholestasis (elevated serum alkaline phosphatase),
AND
- No other immediately apparent possible causes of AT elevation and hyperbilirubinemia, including, but not limited to, viral hepatitis, pre-existing chronic or acute liver disease, or the administration of other drug(s) known to be hepatotoxic.

9.2.8 Other Safety Considerations

Any significant worsening noted during interim or final physical examinations, electrocardiogram, x-ray filming, any other potential safety assessment required or not required by protocol should also be recorded as a nonserious or serious AE, as appropriate, and reported accordingly.

9.3 Overdose

An overdose is defined as the accidental or intentional administration of any dose of a product that is considered both excessive and medically important. All occurrences of overdose must be reported as SAEs (see [Section 9.2](#)).

9.4 Safety

Planned time points for all safety assessments are listed in the Schedule of Activities (see [Section 2](#)).

9.4.1 Clinical Safety Laboratory Assessments

Investigators must document their review of each laboratory safety report.

Hematology (CBC)
Hemoglobin
Hematocrit

Total leukocyte count, including differential	
Platelet count	
Prothrombin time (PT)/ International normalized ratio (INR)	
Partial thromboplastin time (PTT)	
Chemistry	
Aspartate aminotransferase (AST)	Sodium (Na)
Alanine aminotransferase (ALT)	Potassium (K)
Total bilirubin	Chloride (Cl)
Alkaline phosphatase	Calcium (Ca)
Lactate dehydrogenase (MLR)	Corrected calcium (Screening only)
Creatinine	Phosphorus (P)
Blood Urea Nitrogen (BUN)	Magnesium (Mg)
Glucose	Amylase
Albumin	Lipase
Urinalysis	
Creatinine	
Protein	
Urine protein/creatinine ratio (UPCR)	
Serology	
Serum for hepatitis C antibody, HCV RNA, hepatitis B surface antigen (screening only). HIV, if mandated locally. (Sites in Germany, see Appendix 12)	
Other Analyses	
Thyroid stimulating hormone (TSH) with free thyroxine (fT3) and free triiodothyronine (fT4) (screening only); TSH with reflexive fT3 and fT4 during study and follow up	
Pregnancy test (WOCBP only: screening and during study)	
Follicle stimulating hormone (FSH) (screening only for women under 55 years old to confirm menopause as needed)	

9.4.2 *Imaging Safety Assessment*

Any incidental findings of potential clinical relevance that are not directly associated with the objectives of the protocol should be evaluated and handled by the Study Investigator as per standard medical/clinical judgment.

[Redacted text block]

[Redacted text block]

[Redacted text block]

[Redacted text block]

[Redacted text block]

[Redacted text block]

[REDACTED]

[REDACTED]

[REDACTED]

[REDACTED]

[REDACTED]

[REDACTED]

[REDACTED]

[REDACTED]

[REDACTED]

[REDACTED]

[REDACTED]

[REDACTED]

[REDACTED]

[REDACTED]

[REDACTED]

[REDACTED]

[REDACTED]

[REDACTED]

[REDACTED]

[REDACTED]

[REDACTED]

[REDACTED]

[REDACTED]

[REDACTED]

[REDACTED]

[REDACTED]

[REDACTED]

[REDACTED]

[REDACTED]

9.9 Health Economics OR Medical Resource Utilization and Health Economics

Health Economics/Medical Resource Utilization and Health Economics parameters will be evaluated in this study as noted in [Section 2](#).

Medical resource utilization and health economics data, associated with medical encounters, will be collected in the CRF by the investigator and study-site personnel for all participants throughout the study. Protocol-mandated procedures, tests, and encounters are excluded.

The data collected may be used to conduct exploratory economic analyses and will include:

- Number and duration of medical care encounters, including surgeries, and other selected procedures (inpatient and outpatient)
- Duration of hospitalization (total days length of stay, including duration by wards; eg, intensive care unit)
- Number and character of diagnostic and therapeutic tests and procedures
- Outpatient medical encounters and treatments (including physician or emergency room visits, tests and procedures, and medications)].

10 STATISTICAL CONSIDERATIONS

10.1 Sample Size Determination

The sample size of this study accounts for the primary endpoint of progression-free survival (PFS) per BICR in all randomized participants. Assuming a 25% screen failure rate, it is expected that approximately 850 participants will need to be enrolled in order to randomize 638 participants (319 per arm) in a 1:1 ratio. To represent the normal frequency of the favorable risk group in mRCC, the favorable risk participants are capped at approximate 25%; thus, at most 212 favorable risk participants (106 per arm) will be enrolled to randomize 160 favorable risk participants in a 1:1 ratio. The rest of the enrolled participants will provide approximately 478 intermediate/poor risk randomized participants (239 per each arm).

The overall alpha for this study is 0.05 (two-sided). PFS will be evaluated for treatment effect at an alpha of 0.05 (two-sided), with at least 95% power. No interim analysis of PFS is planned. OS will be evaluated for treatment effect at an alpha level of 0.05 (two-sided) with 80% power, accounting for two formal interim analyses to assess efficacy.

Sample Size Justification for Primary PFS Endpoint

The primary endpoint of PFS per BICR of Arm A versus Arm C analysis will be conducted on all randomized participants. The PFS analysis will occur after approximately 9-10 months minimum follow-up on all randomized subjects by which approximately 350 events from Arm A and Arm C are expected. The 350 PFS events provide at least 95% power to detect a HR of 0.68 for PFS of Arm A versus Arm C with a type I error of 0.05 (two-sided). The HR of 0.68 corresponds to a 47% increase in the median PFS, assuming a median PFS of 18.2 months for Arm A and 12.4 months for Arm C. It is projected that an observed HR of 0.811 or less, which corresponds to a 2.89 month or greater improvement in median PFS (12.4 versus 15.3 months), would result in a statistically significant improvement in PFS for the Arm A versus Arm C comparison.

If the formal analysis of PFS among all randomized participants is statistically significant, the formal interim analysis of OS among all randomized participants will be tested, as per hierarchical testing procedure.

Sample Size Computation for Secondary OS Endpoint

The secondary endpoint of OS in all randomized participants specifies the comparison of Arm A versus Arm C. Among all randomized participants, approximately 254 events (ie, deaths) in Arm A and Arm C provides at least 80% power to detect a HR of 0.70 for OS of Arm A and Arm C with an overall type 1 error of 0.05 (two-sided) for each test. The HR of 0.70 corresponds to a 43% increase in the median OS, assuming a median OS of 47.1 months for Arm A and 33 months for Arm C.

Two formal interim analyses of OS are planned for this study. The first interim analysis is planned at the time of final PFS analysis and it is expected to observe 165 OS events (65% of the targeted OS events for final analysis) and the second interim analysis is planned to occur after observing approximately 211 events (83% of targeted OS events needed for final analysis). The stopping boundaries at interim and final analyses will be derived based on the number of deaths using O'Brien and Fleming α spending function. For example, with 165, 211, and 254 observed events in Arm A and Arm C at the first interim, second interim, and final analyses, the respective stopping boundaries would be $\alpha=0.011$ (two-sided), $\alpha=0.025$ (two-sided), and $\alpha=0.041$ (two-sided). If the first interim analysis is performed exactly at 165 deaths, it is projected that an observed HR of 0.673 or less, which corresponds to a 16.0 month or greater improvement in median OS (33 versus 49 months), would result in a statistically significant improvement in OS for the Arm A versus Arm C comparison. At the second interim analysis with 211 deaths, it is projected that an observed HR of 0.734 or less, which corresponds to a 12.0 month or greater improvement in median OS (33 versus 45 months), would result in a statistically significant improvement in OS for the Arm A versus Arm C comparison. At the time of final OS analysis when there are 254 deaths, it is projected that an observed HR of 0.774 or less, which corresponds to a 9.6 month or greater improvement in median OS (33 versus 42.6 months), would result in a statistically significant improvement in OS for the Arm A versus Arm C comparison.

Assuming a constant accrual rate (an average rate of 3 participants/month in the first 4 months, afterwards an average rate of 42 participants/month), the accrual will take approximately 19 months. The final PFS analysis will not occur prior to these conditions being met:

- at least 8 months minimum follow-up on all randomized subjects;
- at least 283 PFS events, which provide at least 90% power to detect a HR of 0.68 for PFS of Arm A versus Arm C; and
- at least 149 OS events, which provide 66% power if the target HR for OS was 0.60. (Note that if the analysis of first interim analysis OS takes place with 149 OS events, the alpha spending for the OS comparison would be 0.007 with a critical HR=0.643.)

This expected PFS analysis will occur at approximately 29 months from FPFV. The second interim and final analyses of OS are expected to occur approximately 34 months and 40 months from FPFV, respectively. Table 10.1-1 summarizes the results of these calculations.

Table 10.1-1: Summary of sample size parameters and schedule of analyses

Primary/Secondary Endpoints	PFS (Primary)	OS (Secondary) ^a
Primary analysis population	All Randomized Participants	
Accrual rate per month for all randomized population	3 participants/month in the first 4 months, afterwards an average rate of 42 participants/month	
Power	95%	80%
Alpha	0.05 2-sided	0.05 2-sided (0.011 at IA1, 0.025 at IA2, 0.041 at FA)
Hypothesized median control vs exp (months)	12.4 vs 18.2	33 vs 47.1
Hypothesized hazard ratio	0.68	0.70
Critical hazard ratio (observed hazard ratio at which a statistically significant difference would be observed) / Difference in median (months) Corresponding to a minimal clinically significant effect size (FA) ^b	0.811 / 2.89	0.774 / 9.6
Critical HR at interim analysis-1(IA1) /effect size	N/A	0.673 / 16.0
Expected number of event for IA1 (percentage of target events)	N/A	165 (65%)
Timing of IA1 from FPFV (months)	N/A	29
Critical HR at interim analysis-2(IA2) /effect size	N/A	0.734 / 12.0
Expected number of event for IA2 (percentage of target events)	N/A	211 (83%)
Timing of IA2 from FPFV (months)	N/A	34
Accrual duration (months)	19	19
Timing of final analysis (FA) from FPFV (months)	29	40
Sample size	638	638

Table 10.1-1: Summary of sample size parameters and schedule of analyses

Primary/Secondary Endpoints	PFS (Primary)	OS (Secondary) ^a
Target number of events (Event Goal)	350	254

^a OS analyses is participant to significance in hierarchical testing strategy for each pairwise comparison.

^b The difference in median (months) only applies if the control group median is exactly as hypothesized.

10.2 Populations for Analyses

All analyses will be performed using the treatment arm as randomized (intent to treat), with the exception of dosing and safety, for which the treatment arm as received will be used. For purposes of analysis, the following populations are defined in Table 10.2-1, and all populations for analyses given in this table refer to those participants in Arm A and Arm C. Those participants who randomized to Arm B prior to Revised Protocol 01 will be considered as part of the population of interest for descriptive summary of efficacy and safety analyses.

Table 10.2-1: Populations for Analyses

Population	Description
All Enrolled Participants	All participants who sign informed consent and were registered into the IRT.
All Randomized Participants	All participants who were randomized will be used for the analysis of demography, protocol deviations, baseline characteristics, primary efficacy analysis, secondary efficacy analyses, and outcome research analysis which will be performed for this population.
All Treated Participants	All participants who received at least one dose of any study medication. This is the primary population for exposure and safety analyses.
[REDACTED]	[REDACTED]
[REDACTED]	[REDACTED]
[REDACTED]	[REDACTED]

10.3 Statistical Analyses

The statistical analysis plan will be developed and finalized before database lock and will describe the selection of participants to be included in the analyses, and procedures for accounting for missing, unused, and spurious data. Below is a summary of planned statistical analyses of the primary and secondary endpoints. A description of the participant population will be included in the statistical output reported, including subgroup of age, gender, and race.

10.3.1 Efficacy Analyses

The efficacy analyses will be performed in all randomized participants in Arm A and Arm C. Descriptive summary of efficacy will be provided for participants randomized in Arm B.

Table 10.3.1-1: Efficacy Analyses

Endpoint	Statistical Analysis Methods
Primary	
The primary endpoint of this study is to compare PFS per BICR of Arm A (doublet) versus Arm C (single agent), in all randomized participants.
 
PFS is defined as the time between the date of randomization and the first date of the documented progression, or death due to any cause, whichever occurs first. Participants who die without a reported progression (and die without start of subsequent anti-cancer therapy) will be considered to have progressed on the date of their death. Participants who did not progress or die will be censored on the date of their last evaluable tumor assessment on or prior to initiation of subsequent anti-cancer therapy. Participants who did not have any on study tumor assessments and did not die will be censored on their date of randomization. Participants who started anticancer therapy (including tumor-directed radiotherapy and tumor-directed surgery) without a prior reported progression will be censored on the date of their last evaluable tumor assessment on or prior to the initiation of first subsequent anti-cancer therapy.
 
The primary formal comparisons of PFS will be conducted using a two-sided 0.05 stratified log-rank test for each comparison, with IMDC scores, PD-L1 tumor expression, and region at screening per IRT as stratification factors among all randomized participants.
 
Median PFS will be estimated via the Kaplan-Meier product limit method. Two-sided 95% CI for the median PFS will be computed for each randomized arm.
 
Kaplan-Meier plots of PFS will be presented. Hazard ratios (HR) and corresponding two-sided 95% confidence intervals (CI) will be estimated using a Cox proportional hazards model, with treatment arm as a single covariate, stratified by the stratification factors, corresponding to the comparison of PFS.
 
The totality of PFS results will be presented in a single graphical display that includes Kaplan-Meier curves for all treatment arms, the log-rank p-values for the formal comparisons, the HRs and corresponding CIs, and the median PFS estimates and corresponding CIs.
 
The following supportive analyses of PFS will also be conducted: A stratified multivariate Cox regression model will be used in order to estimate the treatment effect after adjustment for possible imbalances in known or potential prognostic factors. The covariates included in this model will be specified in the statistical analysis plan. PFS using an un-stratified log rank test. The hazard ratio associated with treatment will be presented along with the associated two-sided 95% CIs. PFS accounting for missing tumor assessment prior to PFS event (progression or death). This analysis will be performed only if at least 10% of events have missing prior tumor assessment. It will apply the following restriction to the primary definition: If the elapsed time between the PFS event and the last assessment immediately prior to the event is two or more missed visits (more than 12 weeks - 10 days), the participant’s PFS will be censored at his/her last tumor assessment prior to the PFS event.

Secondary	
The first secondary endpoint is to compare OS of Arm A versus Arm C in all randomized participants. OS is defined as the time between the date of randomization and the date of death due to any cause. A participant who has not died will be censored at the last known alive date.
 
At the time of the primary endpoint analysis, there will be a first interim analysis of OS. The second interim analysis and the final analysis of OS are planned to occur approximately 34 months and 40 months from FPFV, respectively. OS will be compared between these treatment arms using a two sided, 0.05 level log-rank test (adjusted for interim analyses), stratified using IMDC scores, PD-L1 tumor expression, and region at screening as

Table 10.3.1-1: Efficacy Analyses

Endpoint	Statistical Analysis Methods
	
stratification factors among all randomized participants. A similar analysis as in PFS will be conducted for OS. Hazard ratio (HR) and corresponding two-sided 95% confidence intervals (CI) will be estimated using a Cox proportional hazards model, with treatment arm as a single covariate, stratified by the stratification factors, corresponding to the comparison of OS.
 
The second secondary endpoint evaluates ORR per BICR for all randomized participants. ORR is defined as the proportion of randomized participants who achieve a best response of complete response (CR) or partial response (PR) using the RECIST 1.1 criteria. Best overall response.
 
(BOR) is defined as the best response designation recorded between the date of randomization and the date of objectively documented progression per RECIST 1.1 or the date of subsequent therapy (including tumor-directed radiotherapy and tumor-directed surgery), whichever occurs first. For participants without document progression or subsequent therapy, all available response designations will contribute to the BOR assessment. Duration of response (DOR) is defined as the time between the date of first confirmed documented response (CR or PR) to the date of first documented tumor progression (per RECIST 1.1) or death due to any cause, whichever occurs first. Participants who neither progress nor die will be censored on the date of their last tumor assessment. Responders who started anti-cancer therapy without a prior reported progression will be censored on the date of their last evaluable tumor assessment prior to the initiation of first subsequent anti-cancer therapy. TTR is defined as the time from randomization to the date of the first confirmed documented response (CR or PR), as assessed by BICR. DOR and TTR will be evaluated for responders (CR or PR) only.
 
Tumor assessments are scheduled to be performed at Week 12 following randomization, every 6 weeks for the first 12 months and then every 12 weeks until progression.
 
ORR will be analyzed at the time of the final PFS analysis. ORRs and corresponding 95% exact CIs will be calculated using the Clopper Pearson method within each treatment arms. An estimate of the response rate and an associated exact two-sided 95% CI (Clopper and Pearson) will be presented, by treatment group. Sensitivity analysis based on investigator-determined ORR may also be performed. DOR and TTR will also be evaluated.

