Tumor Assessments	First tumor assessment post-baseline should be performed Week 12 (± 7 days) following randomization. Use same imaging method as was used at baseline. Subsequent tumor assessments should occur at every 6 weeks (± 7 days) until Week 60, then every 12 weeks (± 14 days) until radiographic progression, assessed by the investigator and confirmed by the BICR.		CT/MRI of the chest, abdomen, pelvis, and all known sites of disease. Tumor assessments should be performed at the specified time points regardless of dosing delays. See Section 9.1 for additional details. Treatment Beyond Progression A radiographic assessment/ scan should be performed within 6 weeks of initial investigator-assessed progression. Refer to Section 8.1.4 for tumor assessment associated with Treatment beyond progression.
[REDACTED]			
[REDACTED]	■	■	[REDACTED]
[REDACTED]	■	■	[REDACTED]
[REDACTED]			
[REDACTED]	■		[REDACTED]
[REDACTED]	■	■	[REDACTED]

Table 2-2: On Treatment Procedural Outline for Arm A Nivolumab Combined with Cabozantinib, Doublet (CA2099ER)

Procedure	Cycle 1, Day 1 Cycle=2 wks	C2 and subsequent visits ^a Each Cycle=2 wks	Notes
Randomize	X		Begins with call to Interactive Response Technology (IRT). Participants must have an evaluable PD-L1 result from the central lab in order to be randomized.
Administer Nivolumab and Cabozantinib	X	X	See Section 7 . Dispense study treatment as appropriate. Day 1 Treatment must begin within 3 days (72 hours) of Randomization)

Abbreviations: C=cycle; D=day; wks= weeks. For abbreviations on lab tests refer back to [Section 9.4.1](#).

Notes: Some of the assessments referred to in this section may not be captured as data in the eCRF. They are intended to be used as safety monitoring by the treating physician. Additional testing or assessments may be performed as clinically necessary or where required by institutional or local regulations.

^a If a dose is delayed, the procedures scheduled for that same timepoint should also be delayed to coincide with when that timepoint's dosing actually occurs.

Table 2-3: On Treatment Procedural Outline for Arm B Nivolumab and Ipilimumab Combined with Cabozantinib, Triplet (CA2099ER)

CA2099ER Global Revised Protocol 01

Implementation of CA2099ER Global Revised Protocol 01 stops further randomization into Arm B. Participants previously randomized to Arm B continue with Arm B treatment and continue with Arm B clinical planned events, per protocol.

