9.1.2.1 Investigator Assessment of Progression

The same method of assessment used at Screening should be used for on-study time points. Brain MRI or CT scans during on-study time points and the follow-up phase are only required in participants with a history of CNS metastases prior to randomization or if clinically indicated for new signs or symptoms that suggest new or worsening CNS metastases.

Post-baseline tumor assessments will be performed at the time points described below until progression assessed by the investigator **and** confirmed by BICR, death, or withdrawal from the study, whichever occurs first.

- First tumor assessment post-baseline should be performed at Week 12 (\pm 7 days) following randomization. Use same imaging method as was used at screening/baseline.
- Subsequent tumor assessments should occur at every 6 weeks until Week 60. Allowable window for assessments is \pm 7 days until Week 60. After Week 60, tumor assessments should occur every 12 weeks (\pm 14 days) until radiographic progression, assessed by the investigator **and** confirmed by the BICR.
- Additional imaging of potential disease sites should be performed whenever disease progression or a secondary malignancy is suspected. In participants with no history of brain lesions prior to randomization, brain MRI or CT on-study treatment should be obtained if clinically indicated. Bone imaging during on-study treatment and follow-up periods should be obtained if clinically indicated.
- Tumor assessments are to continue for all randomized participants according to the protocol schedule until radiographic progression has been assessed by the investigator **and** confirmed by the BICR, regardless of whether study drug dosing is delayed, reduced, or discontinued.

The investigator (in consultation with the local radiologist as needed) will complete tumor assessments using RECIST (Response Evaluation Criteria in Solid Tumors) 1.1 criteria on all imaging time points specified in the protocol. Any additional imaging that may demonstrate tumor response or progression, including scans performed at unscheduled time points and/or at an outside institution, should also be collected for the investigator to complete RECIST 1.1 tumor assessments on these images and to submit them for BICR review.

All study treatment decisions will be based on the investigator’s assessment of tumor images and not on the BICR assessment.

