9.1.2.2 BICR Assessment of Progression

Sites should submit all scans to a BICR on a rolling basis, preferably within 7 days of scan acquisition, throughout the duration of the study. BICR will review scans on a rolling basis and remain blinded to treatment arm and investigator assessment of submitted scans. When progression per RECIST 1.1 criteria is assessed by the investigator, the site will inform the imaging core lab, so that the BICR assessment of progression can be performed. The BICR review will be completed and the results provided to the site within approximately 14 days of receipt of the scans, provided there are no pending imaging queries to the site.

Participants whose progression is not confirmed by the BICR will be required to continue tumor assessments (if clinically feasible) according to the protocol-specified schedule or sooner if clinically indicated until the BICR confirms progression on a subsequent tumor assessment. Also, if participants discontinue treatment without radiographic progression, tumor assessments will continue according to the protocol specified schedule, as noted in Section 2, until progression has been confirmed by BICR.

All study treatment decisions will be based on the investigator’s assessment of tumor images and not on the BICR assessment. The BICR assessment of progression is only relevant for determining when tumor assessments for a given participant are no longer required to be submitted to the imaging vendor.

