4 ENDPOINTS

4.1 Primary Endpoints

Progression-free survival (PFS) is the primary endpoint. Two definitions are used for the analysis of PFS. The primary definition accounts for subsequent therapy by censoring at the last evaluable tumor assessment on or prior to the date of subsequent therapy. The secondary definition is irrespective of subsequent therapy and does not account for subsequent therapy.

Clinical deterioration in the absence of unequivocal evidence of progression (per RECIST v1.1 criteria) is not considered progression for purposes of determining PFS.

PFS rate at time T is defined as the probability that a subject has not progressed and is alive at time T following randomization. PFS rates at fixed time points (e.g. 6 months, depending on the minimum follow-up) are defined as the probability that a subject has not progressed and is alive at time T following randomization.

The first on-study tumor assessment is scheduled to be conducted at 12 weeks (± 1 week) following randomization. Subsequent tumor assessments are scheduled every 6 weeks (± 1 week) up to week 60, then every 12 weeks (± 2 weeks) until disease progression.

4.1.1 **Primary Definition of Progression-Free Survival (Accounting for Subsequent Therapy)**

The primary definition of PFS (PFS truncated at subsequent therapy, which includes anti-cancer therapy, tumor directed radiotherapy, or tumor directed surgery) is defined as the time between the date of randomization and the date of first documented tumor progression, based on BICR assessments (per RECIST v1.1 criteria), or death due to any cause, whichever occurs first.

Subjects who die without a reported progression will be considered to have progressed on the date of their death. The following censoring rules will be applied for the primary definition of PFS:

- Subjects who did not progress or die will be censored on the date of their last evaluable tumor assessment.
- Subjects who did not have any on study tumor assessments and did not die will be censored on their date of randomization.

- Subjects who receive subsequent anti-cancer therapy prior to documented progression will be censored at the date of the last evaluable tumor assessment conducted on or prior to the date of initiation of the subsequent anti-cancer therapy.

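### In the supportive missed-scan PFS analysis, the protocol's 74-day limit does not match its own words, two or more missed visits, for progression found at a scan

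*Protocol*

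**What the plan says.** Protocol Table 10.3.1-1 lists, among the supportive PFS analyses, one that accounts for missing tumor assessments. It is conditional: "This analysis will be performed only if at least 10% of events have missing prior tumor assessment". When it runs, a participant is censored at the last assessment before the event if the time between the two "is two or more missed visits (more than 12 weeks - 10 days".

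The scan schedule is given in several places. Protocol Table 2-2 puts the first post-baseline scan at Week 12 (± 7 days), then "every 6 weeks (± 7 days) until Week 60, then every 12 weeks (± 14 days". Protocol 9.1.2.1 agrees: "After Week 60, tumor assessments should occur every 12 weeks". SAP 4.1 has the same timetable: "scheduled every 6 weeks (± 1 week) up to week 60, then every 12 weeks (± 2 weeks) until disease progression". The ORR text in Table 10.3.1-1 restates it more loosely, with Week 12 first and then "every 6 weeks for the first 12 months and then every 12 weeks until progression".

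Two statements limit how far the protocol text can be pressed. Protocol 10.3 introduces it with "Below is a summary of planned statistical analyses of the primary and secondary endpoints". SAP 7.5.2 item 10 visibly carries only a title, about censoring for two missing assessments. It shows no day count and no 10% condition, and redacted text follows it. SAP 7.1 makes p-values from sensitivity analyses descriptive.

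**The concern.** The words count visits, but the bracket sets one fixed gap. The scan interval doubles after Week 60, so a fixed gap cannot mean the same number of missed visits throughout. The value chosen is also shorter than a single 12-week interval.

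The purpose of the analysis is to show whether the PFS result survives removal of events that follow a long unobserved period. A rule that also removes events after one missed scan, or after none, answers a different question and discards information.

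**Working it through.** **1. The plan's figure.** 12 weeks − 10 days = 12 × 7 − 10 = 74 days. No visible text explains the 10 days. Natural candidates for two missed 6-weekly visits give other values: 3 × 42 = 126, 2 × 42 − 7 = 77, 2 × 42 − 14 = 70.

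**2. Gaps on the schedule.** With *m* consecutive visits missed, the scan-to-scan gap is (*m* + 1) × interval, plus or minus the windows at both ends. The interval is 42 days (± 7) to Week 60 and 84 days (± 14) afterwards. The percentages weight every whole-day combination within the windows equally, which is an assumption.

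| Situation | Nominal gap (range), days | Over 74 | Over 94 |
|---|---|---|---|
| 6-weekly, none missed | 42 (28–56) | 0% | 0% |
| 6-weekly, one missed | 84 (70–98) | 93.3% | 4.4% |
| 6-weekly, two missed | 126 (112–140) | 100% | 100% |
| Week 60 to 72, none missed | 84 (63–105) | 82.1% | 15.2% |
| Later, none missed | 84 (56–112) | 77.4% | 20.3% |
| Later, one missed | 168 (140–196) | 100% | 100% |
| Later, two missed | 252 (224–280) | 100% | 100% |

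Example for the second row: there are 15 × 15 = 225 day combinations. The gap is 74 or less when the second scan's offset is at least 10 days below the first's, which happens in 1 + 2 + 3 + 4 + 5 = 15 of them. So (225 − 15)/225 = 93.3%.

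**3. Reading the dash as a plus.** The 94-day column largely repairs the 6-weekly phase. After Week 60 it still flags 15% to 20% of on-time scans and every single miss.

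**4. Whether any single day count could work.** Separating one from two misses needs a cut between 98 and 112 days in the 6-weekly phase and between 196 and 224 days in the 12-weekly phase. These ranges do not overlap. The transition adds a further difficulty: Week 48 to Week 72 with Weeks 54 and 60 missed is (72 − 48) × 7 = 168 days, and Week 60 to Week 84 with only Week 72 missed is (84 − 60) × 7 = 168 days.

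**5. Deaths.** After a 6-weekly scan, visits fall due at days 42 and 84, and the second window opens at 84 − 7 = day 77. A death after day 84 therefore has two visits missed at nominal timing, and only deaths on days 75 to 83 fall short. In that phase words and number nearly agree.

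**6. Baseline.** Randomization to an on-time Week 12 scan is 77 to 91 days. From a baseline scan up to 28 days earlier it is 77 to 119 days. If baseline counted as the last assessment, every on-time Week 12 progression would be censored. The protocol rule does not say whether it counts.

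**7. Illustrative size.** The simulation used exponential PFS with medians 18.2 and 12.4 months, the planned accrual, a cut at 29 months, 10% of scans missed and baseline not counted. Misses were independent, or in runs with a 50% chance that a miss continues. Runs are plausible because, under Protocol 9.1.2.2, participants with unconfirmed progression "will be required to continue tumor assessments (if clinically feasible". Ranges cover nominal or window timing and 0% or 15% deaths.

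- Independent: 62–78 of 331–336 events censored, 7–8% of them truly after two missed visits. With windows and no deaths, 69.5 were censored: 29.6 with no miss, 34.5 with one and 5.4 with two or more (5.4/69.5 = 7.8%).
- Runs: 50–64 of 329–334 censored, 24–28% true.
- The mean HR moved from 0.680 to 0.674 (independent) and from 0.681 to 0.676 (runs). The standard error of log HR rose from 0.111 to 0.125 and 0.123; a visit-count rule gave 0.112 and 0.116.

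**The case against.** The strongest reply is that the operative rule may be one we cannot see. The protocol text is a declared summary, the SAP is where missing data are to be handled, and the visible title of SAP item 10 counts assessments rather than days. This stands. It means the SAP cannot be said to lack a rule, nor can the 74-day version be said to have been programmed. It does not rescue the protocol wording, since a summary should not contradict itself.

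Several stronger readings are tempting and unsupported:

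- **That all such scans are caught.** The windows allow a one-miss gap of 70 to 74 days, or an on-time late gap of 56 to 74 days, which escapes the rule.
- **That deaths are misclassified to the same degree.** In the 6-weekly phase they are not.
- **That the ORR text definitely contradicts Week 60.** If its 12 months run from Week 12, they end near Week 12 + 52 = Week 64 and the last 6-weekly scan is Week 60, as elsewhere. Only counting from randomization creates a conflict, so the sentence is ambiguous.
- **That the 10% condition certainly applies.** It stands in the protocol but not in the visible text of SAP item 10, whereas SAP items 3 and 7 do state 10% conditions.
- **That the simulated counts are predictions.** Missingness was assumed, and censoring at subsequent therapy and dropout were not modelled.

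**Conclusion.** The protocol wording is wrong as written, and the point is minor. For progression found at a scan, the 74-day limit is usually met after one missed scan up to Week 60 and usually met by an on-time scan after it. This part is calendar arithmetic and rests only on the printed schedule; the percentages also assume equal weighting of days within windows.

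If the rule were programmed from the day count, most censored events would have fewer than two missed scans. The size of that effect is illustrative. In the simulation the cost is mainly precision and a result that does not answer its stated question; the hazard ratio hardly moves.

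A reader might infer that the primary PFS result is at risk. The documents do not support that: the analysis is supportive, its p-value is descriptive, and primary PFS, alpha and OS do not depend on it.

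**What to change.** In Protocol Table 10.3.1-1, delete the single day count and censor only when the two scheduled assessments immediately before the event were both missed. On the Week 60 schedule this means:

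- no on-study scan: Weeks 12 and 18 missed, with censoring at randomization;
- last scan at Weeks 12 to 48: the next two 6-weekly visits missed;
- last scan at Week 54: Weeks 60 and 72 missed;
- last scan at Week 60 or later: the next two 12-weekly visits missed.

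Either of two methods would implement this. One assigns each scan to its nearest scheduled visit, with a stated rule for ties and unscheduled scans. The other uses day cut-offs by phase (between 98 and 112, and between 196 and 224) with an explicit rule for the Week 60 transition. For deaths, say which visits count as due, for example those whose window had closed before death.

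State that the baseline scan is not an on-study assessment, and use the same definition for the 10% condition. Check that SAP 7.5.2 item 10 follows the same rule, and align it if not. Clarify in the ORR text that the 6-weekly phase runs to Week 60.

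The cost is a short protocol edit and a check of one SAP item, with SAP edits and reprogramming only if that item uses a different rule. No new data are needed.
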